Low-Level FCT (FCT \leq 12.6) Safety Analysis Set: All Low-Level subjects (FCT \leq 12.6) receiving at least one dose of randomized treatment. Subjects are analyzed under the treatment received. This is the secondary analysis set for safety.

4. Test product, Dose and Mode of Administration

900mg of CM-AT (pancreatic enzyme concentrate encapsulated in hydrogenated soybean oil) 3x daily sprinkled over food. To be taken with a meal or large snack.

5. Demographics, Other Baseline Characteristics (other than efficacy and safety variables), Study Drug Compliance

"Baseline" for variables other than efficacy and safety refers to the last value of the variable measured prior to start of randomized treatment. For efficacy and safety, "Baseline" is defined as the value measured at Screening Part 1, denoted as "Screening" below.

- 5.1 Demographics Baseline demographics of age, gender (male; female), ethnicity (Hispanic or Latino; not Hispanic or Latino), race (American Indian or Alaska Native; Asian; Black or African American; Native Hawaiian or other Pacific Islander); height (cm), weight (kg), body mass index (BMI).
- 5.2 Physical examination abnormalities by body system (HEENT, Respiratory, Cardiovascular, Abdomen, Musculoskeletal, Central Nervous System, Dermatologic, General Appearance, Other)
- 5.3 Responses to each question on Study Specific Medical History questionnaire
- 5.4 Response to each question on Neurodevelopmental history questionnaire
- 5.5 Responses to each question on Family History questionnaire
- 5.6 Responses to each question on Parent Visit questionnaire
- 5.7 Screening ABC-I score. The scoring of this subscale is given in Appendix A.
- 5.8 Screening DSM-IV-TR total score and sub-scores (Social Interaction; Communication; Behavior) as described in Appendix C.

- 5.9 Screening SCQ total score and sub-scores (Social Interaction; Communication; Restricted, Repetitive, and Stereotyped Patterns of Behavior).
 - The total score and the subscales of Reciprocal Social Interaction, Communication, and Restricted, Repetitive, and Stereotyped Patterns of Behavior domain are given in Appendix B.
- 5.10 Screening ADI-R (Total A, Verbal Total B, Nonverbal Total B, Total C and Total D). These scores are determined by the rater and recorded directly on the questionnaire.

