- 5.11 Study Drug compliance will be assessed based upon the sachet usage. The calculation for percentage of compliance is 100 times the number of sachets dispensed at the previous visit minus the number of sachets returned, divided by the days between visits times 3 (not including days after the last visit at which sachets were dispensed if the subject did not return after that last visit). Study drug compliance during the 2-week placebo run-in period and during the randomized double-blind treatment period will be analyzed.

6. Efficacy Variables

The following lists the efficacy variables that will be collected on each subject and analyzed. Section 7 of this document provides the details of the analysis methodology.

- 6.1 **The primary efficacy variable** is the change from Baseline (score at Screening Part 1) to Week 12 in the Aberrant Behavior Checklist (ABC) subscale for Irritability/Agitation (ABC-I) in Low-level FCT ITT subjects. The subscale item components are given in Appendix A. Only the raw scores will be analyzed.
- 6.2 The **secondary efficacy variable** is the change from Baseline (score at Screening Part 1) to Week 12 for the Aberrant Behavior Checklist subscale for Lethargy/Social Withdrawal (ABC-L) in Low-level FCT ITT subjects. The scoring of this subscale is given in Appendix A. Only the raw scores will be analyzed.
- 6.3 Exploratory Efficacy Variables include:
 - Behavioral changes from Baseline (score at Screening Part 1 unless otherwise specified) to Week 12 (the scoring of these subscales is given in Appendix A):

Aberrant Behavior Checklist							
	FCT ≤12.6 U/g	FCT >12.6 U/g	FCT – All Levels				
ABC Irritability		X	X				
ABC Lethargy		X	X				
ABC Hyperactivity	X	X	X				
ABC Stereotypy	X	X	X				
ABC Inappropriate Speech	X	X	X				
ABC Total Score	X	X	X				
Additional Exploratory Endpoints							
Clinical Global Impression – Improvement	X	X	X				
Clinical Global Impression – Severity (Baseline is the value measured at the randomization visit)	X	X	X				
Social Responsiveness Scale ((Baseline is the value measured at the randomization visit)	X	X	X				
Pediatric Quality of Inventory							
Physical Functioning	X	X	X				
Emotional Functioning	X	X	X				
Social Functioning	X	X	X				
Cognitive Functioning	X	X	X				
Communication	X	X	X				
Worry	X	X	X				
Daily Activities	X	X	X				
Total Score	X	X	X				

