8.2 General Statistical Issues

The primary efficacy analysis set is the Low-Level FCT ITT set defined in Section 3. Any efficacy analyses will be presented on other populations from Section 3 will be noted below. The primary safety analysis set is the Low-Level FCT Safety Analysis set. All safety analyses in the double-blind phase will be performed on this analysis set and, secondarily, on the entire Safety Analysis set defined in Section 3.

For quantitative (continuous) variables summaries will include the sample size, mean, median, standard deviation, minimum and maximum. For qualitative (i.e., categorical) variables, summaries will include the number and percent of subjects for each outcome.

Subjects may have a scheduled or unscheduled visit outside the protocol-specified time windows for any protocol-specified visit. Windows of scheduled visits will be expanded to have adjacent start/stop periods so that all visits (scheduled or unscheduled) fall within a scheduled visit window. For example, efficacy data are scheduled to be collected for each subject at screening, Baseline (Screening Part I), Randomization visit, and at Weeks 2, 4, 6, 8, 10 and 12 after randomization. The Week 2 visit will be expanded to allow any visit from 1 – 20 days post-randomization visit to be considered as the Week 2 visit. The Week 4 visit will be expanded to allow any visit from 21 – 34 days post-randomization visit to be considered as the Week 4 visit, etc.

Subjects may have more than one follow-up appointment that falls within a window for a given visit. In such a case, the follow-up data collected closest to the target date the visit should have occurred (given the number of weeks since randomization) will be used in the analysis. If two visits are equidistant from the target date of the scheduled visit, the later visit will be used in the analysis.

Pooling of study centers (i.e., combining study centers with small numbers of patients) may be required prior to performing efficacy analyses that include Study Center as a variable in the analysis. The following is the pooling algorithm that will be used (the algorithm described below is for the Low-Level FCT (≤12.6 U/g) analysis set; the algorithm will be repeated separately for every analysis set on which efficacy data will be analyzed):

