If one or more study centers with Low-Level FCT (≤12.6 U/g) subjects have fewer than 10 subjects for the given analysis population, pooling of study centers will be required. Pooling of small study centers will be implemented as follows;

- Order the study centers, starting with those with the lowest numbers of Low-Level FCT (•12.6 U/g) subjects.
- The centers will then be combined in a consecutive upward order unless the total number of subjects exceeds the median number of subjects of all sites with 10 or more subjects.
- If this process does not capture all the study centers with fewer than 10 subjects, a second pooled study center will be created using the same process.
- This process will be continued until all study centers with fewer than 10 subjects are accounted for.

Again, this pooling algorithm will be repeated separately within each analysis population for which efficacy analyses will be run.

Unless otherwise indicated, p-values are two-sided and statistical significance is declared if the two-sided p-value is ≤ 0.05 . There is only one primary efficacy endpoint and one efficacy secondary endpoint. The primary endpoint will be tested at the two-sided 0.05 level of significance, and if significant, the secondary endpoint will be tested at the two-sided 0.05 level of significance. All other endpoints are considered exploratory and there will be no adjustment for multiple comparisons across these exploratory endpoints.

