For continuous exploratory endpoints, treatments will be compared on change from Baseline in a similar manner as the primary endpoint at Week 12 and each Post-Baseline visit except for multiple imputation and assessment of treatment-by-study center interaction effects. For CGI-S, an endpoint for which there is no Baseline value, treatments will be compared in a similar manner as the primary endpoint on the CGI-S value itself (as opposed to a change from Baseline) without a Baseline value of the endpoint as a covariate. There will be no adjustment for multiple comparisons.

For dichotomous exploratory endpoints (stool test, weight gain/loss), no formal statistical hypothesis testing will be performed to compare the treatment groups on these results.

The number and percentage of subjects experiencing the dichotomous endpoint will be presented for each treatment group. For completeness, this analysis will be repeated for each visit.

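### SAP 6.3 gives CGI-S a Baseline at the randomization visit, but SAP 8.6.3 says it has none and drops the covariate; the CGI-I model is left unclear

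*SAP*

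**What the plan says.** SAP Section 6.3 lists the exploratory efficacy variables under a heading that sets a default and allows exceptions: "Behavioral changes from Baseline (score at Screening Part 1 unless otherwise specified) to Week 12". Section 5 gives the same default, in that Baseline for efficacy and safety "is defined as the value measured at Screening Part 1". Two rows of the 6.3 table use the exception:

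- CGI-Severity: "Severity (Baseline is the value measured at the randomization visit".
- SRS: "Social Responsiveness Scale ((Baseline is the value measured at the randomization visit".

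The CGI-Improvement row has no note.

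Section 8.6.3 gives the models. The general rule is: "For continuous exploratory endpoints, treatments will be compared on change from Baseline in a similar manner as the primary endpoint". The primary model in Section 8.6.1 includes the Baseline score as a covariate, so the rule brings that covariate with it. One scale is then exempted: "For CGI-S, an endpoint for which there is no Baseline value, treatments will be compared in a similar manner as the primary endpoint". For that scale the response is the score itself, and its Baseline is left out of the model. SRS gets no such exemption, and CGI-I is not mentioned.

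Section 8.2 names the randomization visit as a time of efficacy collection ("efficacy data are scheduled to be collected for each subject at screening, Baseline (Screening Part I), Randomization visit"), without saying which scales are rated then. It also says of everything beyond the primary and secondary endpoints: "All other endpoints are considered exploratory".

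**The concern.** The two sections disagree on whether a CGI-S Baseline exists, on the response variable and on the covariate. A programmer cannot satisfy both. SRS makes the conflict plainer: two endpoints with the same stated Baseline are sent to different models.

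CGI-I has a related gap. If it counts as continuous, the general rule asks for change from Baseline, and only the Screening Part 1 default supplies one; no section describes a CGI-I rating at that point. If it does not count as continuous, it is not among the dichotomous endpoints that 8.6.3 names either, so it has no stated model.

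Two things are at stake. One is precision on CGI-S, if a baseline is collected and then not used. The other is having a single pre-specified model for each CGI scale. Section 8.6 applies the efficacy analyses to every ITT, All Randomized and PP set. Each comes in low-level, non-low-level and overall form, so the ambiguity recurs in 3 × 3 = 9 analysis sets.

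**Working it through.** The plan gives no figure to reproduce here. The check is a comparison of the text, followed by an illustration of what the covariate is worth.

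**1. The sections side by side**

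| Scale | Baseline per SAP 6.3 | Model per SAP 8.6.3 | Consistent? |
|---|---|---|---|
| CGI-S | Randomization-visit value | Said to have no Baseline; raw score, no baseline covariate | No |
| SRS | Randomization-visit value | General rule: change from Baseline, with covariate | Yes |
| CGI-I | No note; only the Screening Part 1 default reaches it | Not named; general rule if treated as continuous | Unclear |

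**2. Can the CGI-S statements be reconciled?** One could read 8.6.3 as meaning only that CGI-S has no Screening Part 1 value. That fails on two counts. The 6.3 heading permits a different Baseline where one is specified, and the CGI-S row specifies one. SRS is in the same position, yet 8.6.3 treats it as having a Baseline.

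**3. Does change versus raw score matter?** Let Y be the Week 12 score, B the baseline, T the treatment indicator and τ the treatment effect. If Y − B = μ + τT + βB, then Y = μ + τT + (β + 1)B. With B in the model, τ is the same either way. What matters is whether B is in the model.

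**4. What the covariate is worth.** Let ρ be the correlation between the randomization-visit and Week 12 CGI-S scores. The documents do not give it, so the values below are assumptions. Relative to the raw-score model without baseline:

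- residual variance is multiplied by 1 − ρ²;
- confidence-interval width is multiplied by √(1 − ρ²).

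| Assumed ρ | 1 − ρ² | Variance reduction | √(1 − ρ²) | Interval narrower by |
|---|---|---|---|---|
| 0.3 | 0.91 | 9% | 0.954 | 4.6% |
| 0.5 | 0.75 | 25% | 0.866 | 13.4% |
| 0.7 | 0.51 | 49% | 0.714 | 28.6% |

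This is an approximation for one baseline and one visit. It ignores the study-center term and missing visits. No figure is offered for CGI-I.

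**5. A side effect on LOCF.** Section 8.6.3 exempts exploratory endpoints only from multiple imputation and the treatment-by-center assessment, so the LOCF analysis in 8.6.1 appears to carry over. That analysis may carry forward a Baseline or randomization-visit score. Whether such a CGI-S score exists therefore affects it too.

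**The case against.** The strongest reply is that this is a slip of wording and not an inferior analysis. CGI-S in 8.6.3 may have been meant to read CGI-I. In that case CGI-S follows the general rule with its randomization-visit value as covariate, CGI-I is analysed as the score itself, no baseline is discarded and the CGI-I gap closes. If instead the note in 6.3 is the mistake, there is no baseline to lose. Precision is lost only if 6.3 is right and 8.6.3 is also followed as written.

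That is fair as an account of the harm. The swap is a likely explanation, but nothing in the documents confirms it, and the SAP as written tells the programmer to omit the covariate. The contradiction has to be resolved under any of these readings.

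Three further points stand as limits:

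- The correlations are assumed. The upper end of the range is not an estimate for this trial.
- Randomization keeps the unadjusted comparison unbiased, so only precision is affected.
- The CGI-I point is weaker than the CGI-S point. It is an omission and not a contradiction. The protocol text available is essentially a synopsis without a visit-by-visit assessment schedule, so the absence of a described CGI-I Baseline is limited evidence.

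**Conclusion.** The concern holds. Sections 6.3 and 8.6.3 of the current SAP contradict each other on whether CGI-S has a Baseline, and this is clear from the text alone. That the CGI-I model is not clearly specified also holds, though with less certainty about what was intended.

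The consequence is small. If a randomization-visit CGI-S score is collected and 8.6.3 is followed, CGI-S intervals would be wider than they need be. The adjusted interval would be about 5% to 29% narrower under assumed correlations of 0.3 to 0.7. The primary and secondary tests, the significance level, the sample size and the success criterion do not depend on either CGI scale. This is a worthwhile correction, not a threat to the trial's conclusions.

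**What to change.** Before unblinding, the sponsor should confirm from the assessment schedule whether CGI-S is rated at the randomization visit, and then reconcile the two sections.

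- **If it is collected, as 6.3 says:** amend 8.6.3 to read along these lines: *CGI-S is analysed as change from the randomization-visit value, with that value as covariate. CGI-I is analysed as the value itself, without its own baseline as covariate.*
- **If it is not collected:** correct the note in the CGI-S row of 6.3, keep the raw-score model, and still state the CGI-I model in 8.6.3. If CGI-I is scored in some way the available documents do not describe, that sentence should follow the actual scoring.

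The cost is one or two sentences in the SAP and the matching table programs. No new data collection is needed if 6.3 is right.

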8.7 Safety Analyses

The safety analysis will be performed on the Run-in Safety Analysis Set (run-in phase safety data only) where specified, on the Low-Level FCT Safety Analysis set (for double-blind safety data) and on the entire Safety Analysis set (for double-blind safety data). All subjects receiving at least one dose of randomized treatment is the primary safety analysis set. There will be no imputation of missing data and there will be no adjustment for multiple comparisons.

Adverse Events – The number and percentage of subjects with TEAEs (Treatment Emergent Adverse Events) will be presented overall and by MedDRA System Organ Class (SOC) and Preferred Term (PT). Patients experiencing more than one occurrence of an event within a given SOC and PT will be counted only once within that SOC and PT, respectively. The analysis will be repeated for serious TEAEs, for TEAEs leading to premature withdrawal and for TEAEs deemed at least possibly related to study drug. No formal statistical hypothesis testing will be performed to compare the treatment groups on incidence of TEAEs.

The number and percentage of subjects with TEAEs will be presented by severity of TEAE (mild/moderate/severe) within each SOC and PT. A subject experiencing more than one occurrence of a TEAE within an SOC or

PT will be categorized under the maximum severity in which the subject experienced the TEAE.

The above will be repeated on the run-in TEAEs. The denominator will be the number of patients receiving placebo in the run-in phase, and there will only be one group analyzed (all patients receiving placebo in the run-in phase).

No formal statistical hypothesis testing will be performed to compare the treatment groups on the proportion of subjects with TEAEs.

Physical exams – The number and percentage of subjects with a clinically significant finding on the physical exams will be presented at each Post-Baseline double-blind visit. No formal statistical hypothesis testing will be performed to compare the treatment groups on the proportion of subjects with clinically significant findings.

Fecal Panel - For Fecal Chymotrypsin, pH and A1-Antitrypsin, descriptive statistics (number of subjects, mean, median, standard deviation, minimum and maximum) of Baseline (Screening Part I), each Post-Baseline visit and the change from Baseline at each Post-Baseline visit will be presented. Treatment groups will be compared on change from baseline at each visit using analysis of covariance adjusting for study center and Baseline. For Fecal Chymotrypsin, the number and percentage of subjects with values >12.6 U/g and \le 12.6 U/g at each visit will be presented. For pH, the incidence rate (number and percentage of subjects) with abnormal outcomes will be presented at each visit. For A1-Antitrypsin, the number and percentage of subjects with values <55 and ≥55 will be presented at each visit. Further, for fecal globin and fecal occult blood the incidence rate (number and percentage of subjects) with abnormal outcomes will be presented at each visit, where abnormal is defined as the variable being "present". No formal statistical hypothesis testing will be performed to compare the treatment groups on these results.

Vital signs – For each of the following measurements: weight (kg), systolic blood pressure (mmHg), diastolic blood pressure (mmHg) and pulse (beats per minute), descriptive statistics (number of subjects, mean, median, standard deviation, minimum and maximum) of Baseline, each Post-Baseline visit and the change from Baseline at each Post-Baseline visit will be presented. No formal statistical hypothesis testing will be performed to compare the treatment groups on these results.

Weight Loss by End of Study - The number and percentage of subjects losing weight by the end of the study will be tabulated for each visit for each treatment group. No formal statistical hypothesis testing will be performed

to compare the treatment groups on the proportion of subjects with weight loss.

9. Interim Efficacy Analysis

An Independent Statistical Group (ISG) will conduct one (1) formal interim efficacy analysis on the primary endpoint when at most 50% of the planned number of total Low-Level FCT All Randomized subjects have completed Week 12 evaluations (the exact timing of the interim analysis will depend on enrollment rate; if enrollment is quicker than anticipated, the interim analysis may take place when <50% of the subjects have completed Week 12 evaluations). The Sponsor, participating clinical investigators and any personnel involved in trial conduct will remain blinded to study treatment. The sole purpose of the interim analysis is to ensure proper power of the study.

The ISG will calculate the conditional power for potentially achieving a statistically significant treatment difference at the final analysis, conditioned on the interim results. The conditional power (CP) formula to be used is:

$$CP = \Phi \left(\frac{c_2 \sqrt{n_2} - z_1 \sqrt{n_1} - \frac{(n_2 - n_1)\Delta}{\sqrt{2\sigma^2}}}{\sqrt{n_2 - n_1}} \right)$$

where Φ is the cumulative distribution function of the standard normal distribution; c_2 is the critical value in the final analysis =1.96 (this critical value corresponds to a one-sided final Type I error rate of 0.025); n_2 is the planned final evaluable sample size per treatment group in the Low-Level FCT All Randomized group (=82); z_1 is the test statistic based on the observed interim data (=z-test statistic for the treatment effect from the MMRM model); n_1 is the sample size per group on which the interim observed rates are based (since the sample sizes may not exactly be equal between treatment groups at this stage despite the 1:1 randomization, the average of the two group sample sizes will be used as an approximation); σ^2 is the assumption of the within-group variance (this will be set to the interim pooled standard deviation between the groups), Δ is the assumed difference in treatment means under which the conditional power is calculated. This will be set to the estimate based on the interim power calculation.

If the conditional power is between 50% and 90%, the ISG may recommend increasing the final Low-Level FCT All Randomized sample size n_2 in the above CP formula to maintain 90% conditional power, following the algorithm in Chen, DeMets, and Lan $(2004)^1$. Increasing the sample size to maintain CP of 90% at a one-sided 0.025 level of significance only when the CP is greater than 50% does not inflate the Type I error, as shown in Chen, DeMets and Lan if the sample size

Curemark, LLC Protocol No. 00103 Autism

increment is less than 151.3% of the original sample size. The value of 151.3% corresponds to the value of 100*R=100*1.513 in Table IV of Chen, Demets and Lan, where R satisfies:

$$\frac{\sqrt{1+R}\left(\sqrt{1+R}-1\right)}{\sqrt{1+R-t}} = \left(\frac{z_{\beta}}{z_{\alpha}}\right)$$

where t is the information fraction at which the interim analysis is carried out (=0.5) based on the original planned final sample size, z_{β} is the z-critical value corresponding to 90% power (=1.28) and z_{α} is the z-critical value corresponding to a one-sided 0.025 level of significance (or two-sided 0.05 level of significance) = 1.96.

Again, the above assumes t=0.5; note that if t<0.5, the value of R will be revised accordingly. If the Low-Level FCT All Randomized sample size is increased, the entire randomized sample size will be increased accordingly to ensure the required number of Low-Level FCT All Randomized subjects is met; enrollment will not be specifically focused on Low-Level FCT All Randomized subjects.

10. Software

All analyses, data listings and tables will be performed/produced using SAS® version 9.4 or higher.

¹ Chen, JYH, DeMets, DL, Gordon Lan, KK, *Increasing the sample size when the unblended interim result is promising, Statist.* Med. 2004; 23:1023-1038 (DOI: 10.1002/sim.1688)

_

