8.1 Sample Size

Sample size is based on:

- The primary efficacy variable -
 - Change from Baseline (score at Screening Part 1) to Week 12 for the Aberrant Behavior Checklist (ABC) subscale for Irritability
- The primary analysis set of Low-level FCT ITT subjects.
- 1:1 randomization scheme

Previously reported Sponsor data indicating that 60% of autistic children have pathologically low levels of FCT formed the basis for the following calculations. Assuming a -3.7 ± 7.0 ABC Irritability change from Baseline to Week 12 of for CM-AT and -0.6 ± 5.0 for Placebo, a sample size of 82 evaluable low-level subjects per treatment group (active and placebo) yields 90% power to declare a statistically significant difference between treatments at a two-sided 0.05 level of significance. To account for an anticipated 15% early withdrawal, 97 low-level subjects will be randomized per treatment group (active and placebo). A total of 162 subjects per group will be randomized to achieve 97 randomized low-level subjects per group (active and placebo).

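### The SAP Section 9 conditional-power formula puts a standard deviation where a variance belongs and, as printed, takes the wrong tail, so the 50%-90% window for raising the sample size picks out the wrong interim results

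*SAP*

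**What the plan says.** SAP Section 9 plans one unblinded interim analysis by an independent statistical group, when at most half of the planned low-level FCT subjects have completed Week 12. Its only stated purpose is to protect power. The section introduces its equation with "The conditional power (CP) formula to be used is" and prints

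CP = Φ{[c2√n2 − z1√n1 − (n2 − n1)Δ/√(2σ²)] / √(n2 − n1)}.

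The definitions that matter are:

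- "Φ is the cumulative distribution function of the standard normal distribution", so Φ is the lower tail.
- "c_2 is the critical value in the final analysis =1.96 (this critical value corresponds to a one-sided final Type I error rate of 0.025".
- σ² "is the assumption of the within-group variance (this will be set to the interim pooled standard deviation between the groups".
- n2 is 82 per group, and Δ is taken from the interim. No sign convention is given for z1 or Δ.

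The rule that uses the result is: "If the conditional power is between 50% and 90%, the ISG may recommend increasing the final Low-Level FCT All Randomized sample size n_2", so as to keep CP at 90%. The section then says that increasing the sample size "only when the CP is greater than 50% does not inflate the Type I error", provided the increment stays below 151.3% of the original size.

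SAP Section 8.1 codes improvement as a negative change: −3.7 ± 7.0 on CM-AT against −0.6 ± 5.0 on placebo.

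**The concern.** There are two separate faults.

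**(a) Standard deviation for variance.** The formula divides by √(2σ²), which is right only when σ² is a variance. The text calls it one and then assigns it the pooled SD.

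**(b) Tail.** With c2 = +1.96, Φ of the printed argument is the probability that the final statistic falls below 1.96. CP is the probability that it falls above. The Φ form would be valid with c2 = −1.96 and benefit coded negative, but the SAP also gives +1.96 in words.

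This number is the only trigger for enlarging the trial. If it is wrong, truly promising results get no increase and weak ones may get one. The statement that Type I error is not inflated also depends on true CP exceeding 50%, and the printed trigger does not enforce that. Because total enrolment rises with the low-level target, a misplaced increase also randomizes more children with FCT above 12.6.

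**Working it through.** **Inputs.** SAP 8.1: difference 3.1, SDs 7 and 5, so pooled variance (49 + 25)/2 = 37 and pooled SD 6.083. SAP 9: n2 = 82, c2 = 1.96, t = 0.5, so n1 = 41. Assumption: Δ is the observed interim difference, Δ = z1√(2·37/41). Benefit is positive unless stated.

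**The plan's own figures reproduce.** The normal approximation gives n = 81, with power 90.4% at 82 (noncentral t: 90.0%). 82/0.85 rounds up to 97, and 97/0.60 to 162. The SAP's equation for R gives 1.510 with z_β = 1.28 and 1.513 with 1.2816.

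**Reducing the formula.** With Δ at the interim estimate, Δ/√(2σ²) = z1/√n1. At n1 = 41 and n2 = 82 the argument is 1.96√2 − 2z1 = 2.772 − 2z1. Using the SD for σ² multiplies the drift by √6.083 = 2.466, and the argument becomes 2.772 − 3.466z1.

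**Windows for a reading of 50% to 90%** (normal quantile 1.2816):

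| Version | Calculation | z1 window | True CP there |
|---|---|---|---|
| Correct: 1 − Φ, variance | 2.772/2 to (2.772 + 1.282)/2 | 1.39 to 2.03 | 50% to 90% |
| (a) SD slip alone | 2.772/3.466 to 4.053/3.466 | 0.80 to 1.17 | 12% to 33% |
| (b) Printed tail alone | (2.772 − 1.282)/2 to 2.772/2 | 0.75 to 1.39 | 10% to 50% |
| Both (literal text) | 1.490/3.466 to 2.772/3.466 | 0.43 to 0.80 | 3% to 12% |

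The correct window and the slip window do not overlap. Across the correct window, the slip version reads 98% to 100%. For a pooled SD of 5 the true CP limits of the slip window are 14% and 39%; for 7 they are 11% and 29%.

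**Spot values of the reported CP:**

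| z1 | Correct | (a) alone | (b) alone | Both |
|---|---|---|---|---|
| 0 | 0.003 | 0.003 | 0.997 | 0.997 |
| 1.00 | 0.22 | 0.76 | 0.78 | 0.24 |
| 1.70 | 0.735 | 0.999 | 0.27 | 0.0009 |

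- At z1 = 1.70 the intended rule needs n2 of about 130: (1.96√130 − 1.70√41 − 89·1.70/√41)/√89 = −1.29, so CP = 0.90. None of the three faulty versions triggers an increase.
- At z1 = 0.80 the SD slip raises n2 to 142, where its own CP reads 0.90. The true argument there is (1.96√142 − 0.80√41 − 101·0.80/√41)/√101 = 0.56, so true CP is 0.29.
- At the design effect, z1 = 3.1/√(74/41) = 2.31. True CP is 96.7%; the printed tail gives 3.3%.
- For n2 from 83 to the cap of 2.513 × 82 = 206, the largest printed value inside its own window is 0.897 (tail alone) or 0.896 (both). The 90% target is never reached.

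**Benefit negative, as in Section 8.1, with c2 = +1.96.** The printed value is Φ(2.772 + 2|z1|) for a favourable result: 0.997 at z1 = 0 and higher for any benefit. No favourable result enters the window.

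**Other timing or Δ.** For general t the correct argument is (1.96 − z1/√t)/√(1 − t). Under the slip, z1/√t is replaced by z1[√t + 2.466(1 − t)/√t]. At t = 0.4 the correct window is 1.24 to 1.87 and the slip window 0.66 to 0.99, with true CP 12% to 31%. If Δ were instead fixed at 3.1, correct CP at t = 0.5 is Φ(z1 + 2.307 − 2.772), or 0.32 at z1 = 0. The slip gives Φ(z1 + 5.691 − 2.772), already 0.998 at z1 = 0.

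**Operating characteristics** (numerical integration over z1, final critical value 1.96, n2 raised to the version's own 90% target, capped at 206):

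| | No increase | Intended rule | (a) alone |
|---|---|---|---|
| Power at 3.1 | 90.4% | 92.2% | 91.4% |
| Power at 2.2 (assumed) | 63.9% | 68.2% | 66.1% |
| One-sided Type I error | 0.0250 | 0.0236 | 0.0255 |

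The chance of landing in the true 50%-90% zone is 21% at 3.1 and 25% at 2.2. Type I error reaches 0.0256 to 0.0267 only if every increase in a wrong window is forced to the cap.

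**The case against.** The strongest reply has four parts.

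- **The tail fault may come from PDF conversion.** A lost minus sign before 1.96 is less likely, because the value is also given in words. A lost 1 − before Φ is possible. This stands: (b) is certain only for the text as transcribed and should be checked against the source file. It does not touch (a), which is written in prose.
- **The surrounding text shows the intent.** It names a variance, uses √(2σ²) and cites a published algorithm. A competent independent group would notice that a design-effect result cannot have a CP of 3%. That is plausible, but the SAP names this as the formula to be used and raises n2 within it. Correcting it during an unblinded analysis would mean departing from the pre-specified rule.
- **The consequence is limited.** No early stopping for efficacy or futility is specified, the final test is unchanged and the Type I excess is small. This is fair. Under (a) alone the power loss against the intended rule is about 0.8 points at 3.1 and 2.2 points at 2.2. The larger gaps, 1.8 and 4.3 points, apply when no increase results.
- **The exact windows depend on t = 0.5 and on how Δ is read.** They do, and the SAP's wording for Δ is unclear. The direction of the error is the same in the alternatives tried.

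**Conclusion.** The concern holds, and the text must be corrected. As written, Section 9 does not compute the quantity it names. The SD wording alone shifts the increase window from z1 = 1.39-2.03 to 0.80-1.17, where true CP is 12% to 33%. The literal text with both faults shifts it to 0.43-0.80 (true CP 3% to 12%) and cannot reach its own 90% target. No sign convention rescues Φ with c2 = +1.96. The damage is mainly to the power safeguard rather than to Type I error. The claim of no inflation is sound for correctly computed CP above 50%, but this trigger does not secure that condition.

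Confidence is high for (a), and high for (b) on the text as transcribed. The sizes assume n1 = 41, n2 = 82, pooled SD 6.083 and Δ at the interim estimate. The 2.2-point difference is illustrative.

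**What to change.** Amend SAP Section 9 before the interim:

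1. Write CP = 1 − Φ{[c2√n2 − z1√n1 − (n2 − n1)Δ/√(2σ²)] / √(n2 − n1)} with c2 = 1.96 and z1 and Δ signed so that CM-AT benefit is positive. Equivalently, keep Φ with c2 = −1.96 and benefit negative, which matches the coding in Section 8.1. Check the source file for a dropped symbol.
2. State the sign convention in one sentence.
3. Set σ² to the interim pooled variance, that is, the square of the pooled SD.
4. Say plainly that Δ is the observed interim treatment difference, if that is what is meant.
5. Add a check value: z1 = 1.70, n1 = 41, n2 = 82 and Δ at the interim estimate give CP = 0.735.

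The cost is one formula and a few phrases, with no extra data or patients.
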